## 5.7 Analysis Visit Windows and Endpoints

### 5.7.1 Non-Peak Pruritus NRS

For efficacy analyses and safety analyses by visit (NRS excluded), assessments at scheduled and unscheduled visits will be mapped to the appropriate analysis visit window as detailed in [Table 1 Schedule of Events](#).

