Added creatine phosphokinase to list of laboratory parameters	Table 7	Correct oversight
Replaced PK parameter of “oral clearance” with “apparent systemic clearance”	Global	Correct error
Minor edits for grammar (i.e., spelling, punctuation) and consistent terminology	Global	Correct grammatical errors and inconsistencies
Incorporated changes in Administrative Letter 2	Global	Provide clarification

Description of Change	Sections Impacted	Brief Rationale
Global Amendment 1, Version 2.0 (30 March 2023)		
Corrected exclusion criteria numbering	Synopsis	Correct error
Revisions to Schedule of Assessments: 
 Corrected visit window for Week 4 (-2 days) and Week 8/ET (± 2 days) Updated footnote d (on ECG collection) Updated footnote reference and footnote wording for IP administration (footnote h) 	Tables 2 and 3	Correct errors and provide clarification
Added paragraph on dose justification	Section 1.1	Provide clarification
Clarified that the last dose of study treatment on Day 28 is to be applied during the study visit	Section 3.1 (and Synopsis)	Provide clarification
Added statement that participants are not to receive study treatment for more than 28 days	Section 3.1 (and Synopsis)	Provide clarification
Updated inclusion criterion 7 to specify Vitamin C as an exclusionary emollient	Sections 4.1 and 5.2.1 (and Synopsis)	Correct inconsistency with Table 6 (Prohibited Therapies and Procedures)
Updated exclusion criteria 2, 9, 11, and 12 on prior/concomitant therapies; Added exclusion criterion 28	Section 4.2 (and Synopsis)	Correct inconsistency with Table 6 (Prohibited Therapies and Procedures)
Added possible reasons for withdrawal and information regarding loss to follow up	Section 4.3	Provide clarification
Added antihistamines to Table 6 (Prohibited Therapies or Procedures)	Section 5.2.3	Correct inconsistency with exclusion criterion 9
Updated study restrictions to be consistent with other protocol sections	Section 5.4	Correct inconsistency
Removed format for participant ID numbers	Section 5.5	Correct error
Removed Appendices and referenced their inclusion in the Investigator site files	Sections 7 and 12	Limit distribution of duplicative information
Added respiration rate to vital sign assessments	Section 8.1.1	Correct oversight
Minor edits for grammar (i.e., spelling, capitalization, punctuation) and abbreviation use	Global	Correct grammatical errors and inconsistencies

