Using analysis outlined above for the primary endpoint, N=24/cohort will give 80% power to detect a standardized effect of 0.72 with 2-sided significance level of 0.1 (28.8% improvement over placebo in percent change from baseline in pruritus, assuming SD = 40%).

Table 2 Schedule of Events

Study Visits	Screening (up to D-28)	Randomization ^a (phone)	Treatment Period					Follow-up/ET (Day 56/Week 8)
			D1	D8 (Week 1)	D15 (Week 2)	D22 (Week 3)	D28 (Week 4)	
Window (days)			0 days	±1 day	±2 days	±2 days	-2 days	±2 days
Informed consent	X							
Demographics	X							
Medical and surgical history	X		X					
Inclusion-exclusion criteria	X		X					
Pregnancy test (WOCBP only)	Serum		urine	urine	urine	urine	urine	urine
Clinical laboratory tests (biochemistry, hematology, urinalysis)	X		X		X		X	X
Body weight and height, BMI ^b	X		X		X		X	X
Serology (HIV, HBV, HCV)	X							
Physical examination	X		X		brief		X	brief
Vital signs	X		X	X	X	X	X	X
Electrocardiogram (12-lead, central reading)	X ^c		X ^d		X		X ^d	X ^e
vIGA	X		X		X		X	X
BSA (excluding palms, scalp, axillae, groin, genitals, and folds)	X		X		X		X	X
EASI	X		X		X		X	X
5-D pruritus scale			X		X		X	X
DLQI			X		X		X	X
POEM			X		X		X	X
Pruritus NRS ^f	X		X	X	X	X	X	
Randomization		X						
Investigational Product Application at study site			X				X	
Investigational Product BID Application Daily ^g			X				X ^g	
Participant Daily e-Diary ^h			X				X	
Investigational product distribution			X	X	X	X		
Collection of investigational product				X	X	X	X	X ^e
Verification of daily diary				X	X	X	X	
Emollient use	-7 days	X ^a	X				X	
Local tolerability assessments			X	X	X	X	X	X
PK samples collection							See Table 3	
Concomitant medication	X	X	X	X	X	X	X	X
Adverse events evaluation	X	X	X					X

BID=twice daily; BMI=body mass index; BSA=body surface area; D=day; DLQI=Dermatology Life Quality Index; EASI=Eczema Area and Severity Index; ECG=electrocardiogram; ET=early termination; HBV=hepatitis B virus; HCV=hepatitis C virus; HIV=human immunodeficiency virus; NRS=numerical rating scale; PK=pharmacokinetics; POEM =Patient-Oriented Eczema Measure; vIGA= Validated Investigator Global Assessment; WOCBP=women of childbearing potential.

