## **1 INTRODUCTION**

This statistical analysis plan was drafted for the study protocol ASN008-201 “A Randomized, Double-Blind, Vehicle-Controlled, Phase 2 Trial to Evaluate the Anti-pruritic Efficacy, Safety, Tolerability, and Pharmacokinetics of ASN008 in Adults with Mild to Moderate Atopic Dermatitis”. In this document, the contents and methods of statistical analysis will be described in detail.

This statistical analysis plan was based on ASN008-201 Protocol Version 3.0, 05 July 2023 and Case Report Form version 8.0, 31 August 2023.

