### 3.2 Schedule of Events

**Table 1 Schedule of Events**

Study Visits	Screening (up to D-28)	Randomization a (phone)	Treatment Period					Follow-up/ET (Day 56/Week 8)
			D1	D8 (Week 1)	D15 (Week 2)	D22 (Week 3)	D28 (Week 4)	
Window (days)			0 days	±1 day	±2 days	±2 days	±2 days	-2 days
Informed consent	X							
Demographics	X							
Medical and surgical history	X		X					
Inclusion-exclusion criteria	X		X					
Pregnancy test (WOCBP only)	Serum		urine	urine	urine	urine	urine	urine
Clinical laboratory tests (biochemistry, hematology, urinalysis)	X		X		X		X	X
Body weight and height, BMI b	X		X		X		X	X
Serology (HIV, HBV, HCV)	X							
Physical examination	X		X		brief		X	brief
Vital signs	X		X	X	X	X	X	X
Electrocardiogram (12-lead, central reading)	X c		X d		X e		X d	X f
vIGA	X		X		X		X	X
BSA (excluding palms, scalp, axillae, groin, genitals, and folds)	X		X		X		X	X
EASI	X		X		X		X	X
5-D pruritus scale			X		X		X	X
DLQI			X		X		X	X
POEM			X		X		X	X
Pruritus NRS g	X		X	X	X	X	X	
Randomization		X						

Study Visits	Screening (up to D-28)	Randomization a (phone)	Treatment Period					Follow-up/ET (Day 56/Week 8)
			D1	D8 (Week 1)	D15 (Week 2)	D22 (Week 3)	D28 (Week 4)	
Window (days)			0 days	±1 day	±2 days	±2 days	±2 days	-2 days
Investigational Product Application at study site			X	X	X	X		
Investigational Product BID Application Daily b			X -----		X		X g	
Participant Daily e-Diary i			X -----		X		X	
Investigational product distribution			X	X	X	X		
Collection of investigational product				X	X	X	X	X f
Verification of daily diary			X	X	X	X	X	X
Emollient use	-7 days	X a	X -----		X			
Local tolerability assessments			X	X	X	X	X	X
PK samples collection			See Table 2					
Concomitant medication	X	X	X	X	X	X	X	X
Adverse events evaluation	X	X	X -----					X

BID=twice daily; BMI=body mass index; BSA=body surface area; D=day; DLQI=Dermatology Life Quality Index; EASI=Eczema Area and Severity Index; ECG=electrocardiogram; ET=early termination; HBV=hepatitis B virus; HCV=hepatitis C virus; HIV=human immunodeficiency virus; NRS=numerical rating scale; PK=pharmacokinetics; POEM=Patient-Oriented Eczema Measure; vIGA= Validated Investigator Global Assessment; WOCBP=women of childbearing potential.

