### 5.6 Handling of Retests, Unscheduled Visits, and Early Termination Data

When retests measurements are done, the retest measurement will be used for the summary analysis. All data from all visits will be listed.

Unscheduled visit assessment will be listed and will not be included in by-visit outputs.

All safety data will be included in the non-by-visit summary tables/figures. Besides, data from unscheduled visits will be listed.

Early Termination visit assessments will be summarized as a separate visit in by-visit outputs.

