## **15 CHANGES FROM PROTOCOL**

- Added “analyses of adverse events will include all events reported from the time of informed consent to 28 days after the last dose of study drug” to AE definition.
- Added “receive at least 1 dose of treatment” to the definitions of all the analysis sets.
- Updated the definition of the Per protocol population.
- Updated the analysis of categorical efficacy endpoints to use Fisher exact test instead of the CMH test.

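### The SAP's analysis windows reverse the protocol's Week 4 and Week 8 visit windows, and two SAP rules on unscheduled assessments conflict

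*SAP*

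**What the plan says.** SAP 5.7.1 covers by-visit efficacy and safety analyses other than the NRS. It states that "assessments at scheduled and unscheduled visits will be mapped to the appropriate analysis visit window as detailed in" SAP Table 1, the Schedule of Events, so the window row of that table becomes an analysis rule. For Day 1, Day 8, Day 15, Day 22, Day 28 and Day 56, in that order, the row reads "0 days ±1 day ±2 days ±2 days ±2 days -2 days". Both header rows of the table give the same values.

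The corresponding row of Protocol Table 2 reads "0 days ±1 day ±2 days ±2 days -2 days ±2 days". The SAP introduction says: "This statistical analysis plan was based on ASN008-201 Protocol Version 3.0, 05 July 2023". SAP Section 15 lists four changes from the protocol (the adverse event period, the dosing condition in the analysis sets, the per-protocol definition, and Fisher's exact test). None concerns visit windows.

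On unscheduled assessments, SAP 5.6 says: "Unscheduled visit assessment will be listed and will not be included in by-visit outputs". It also says: "All safety data will be included in the non-by-visit summary tables/figures".

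**The concern.** The last two windows are interchanged between two current documents. The protocol values appear deliberate: its version summary records, under Global Amendment 1, that these two windows were corrected to what Table 2 now shows. The SAP also disagrees with itself, because its PK sampling table gives Day 28 as -2 days.

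Other parts of the SAP schedule look older than protocol v3.0. It still shows on-site product application at Days 8, 15 and 22, and diary verification at Days 1 and 56, neither of which is in Protocol Table 2. An outdated table carried forward is the likeliest explanation. It would be harmless as background, but 5.7.1 makes the table operative.

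Three things are at stake:

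- **Week 8.** A compliant visit on Day 57 or 58 falls in no window, and the SAP does not say what happens to it. Its laboratory, vital-sign, brief physical examination and local tolerability results could be left out of Week 8 by-visit tables. The laboratory and vital-sign shift tables (SAP 14.2 and 14.3) count only participants with a baseline result and a result at the specified visit.
- **Week 4.** Assessments on Days 29-30 fall after the 28-day treatment limit but would count as Week 4 for EASI, BSA, vIGA, 5-D, DLQI and POEM. Emollient rules also differ by then: Protocol 3.2.1 has emollient applied to lesions in follow-up, but not to treated areas during treatment.
- **Unscheduled data.** Sections 5.6 and 5.7.1 give different by-visit datasets from the same records, and nothing fixes the choice before unblinding.

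**Working it through.** **Inputs.** Nominal days and windows come from Protocol Table 2 and SAP Table 1. Study day is numbered as in SAP 5.3, with the first treatment date as Day 1. Each window is the set of days from nominal day minus the lower allowance to nominal day plus the upper allowance.

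| Visit | Protocol v3.0 | SAP Table 1 | Difference |
|---|---|---|---|
| Day 1 | 1 | 1 | none |
| Week 1 | 8 ±1 = 7-9 | 7-9 | none |
| Week 2 | 15 ±2 = 13-17 | 13-17 | none |
| Week 3 | 22 ±2 = 20-24 | 20-24 | none |
| Week 4 | 28 -2 = 26-28 (3 days) | 28 ±2 = 26-30 (5 days) | SAP adds Days 29, 30 |
| Week 8 | 56 ±2 = 54-58 (5 days) | 56 -2 = 54-56 (3 days) | SAP omits Days 57, 58 |

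**Week 8.** 5 - 3 = 2 of the 5 permitted days have no SAP window.

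**Week 4.** 5 - 3 = 2 of the 5 SAP days lie outside the protocol window.

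**Scale.** The documents give no visit-timing data. Assume that all of about 120 participants attend follow-up and that a share p attends on Days 57-58. The number with no mapped Week 8 record, on a literal reading, is 120 × p:

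- p = 0: 0
- p = 0.10: 12
- p = 0.20: 24
- p = 0.40: 48 (an even spread over Days 54-58, since 2/5 = 0.40)

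These shares are assumptions, not trial data. Full attendance makes the counts upper values for each share. SAP 5.6 summarizes early-termination assessments as a separate visit, so participants who stop early would not contribute to Week 8.

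**Unscheduled assessments.** Take a repeat EASI at an unscheduled visit on Day 16. Under 5.7.1 it maps to Week 2 (Days 13-17). Under 5.6 it is listed only. Both rules cannot be followed.

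Correcting the windows does not settle this. Under the protocol windows, Days 2-6, 10-12, 18-19, 25 and 29-53 belong to no visit. That is 5 + 3 + 2 + 1 + 25 = 36 of Days 1-58. A rule that maps unscheduled data must therefore also say what happens between windows.

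**What is not affected.** SAP 5.7.2 sets the NRS weeks by study day (Week 4 is Days 22-28), so the primary endpoint and the weekly NRS endpoints do not use Table 1. No efficacy endpoint in SAP Section 2 is defined at Week 8.

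**The case against.** The mismatch itself is hard to dispute. The best counter-case concerns its consequences.

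First, an analysis window wider than the conduct window is a legitimate choice, because it keeps a late Week 4 assessment that would otherwise be lost. The protocol allows no Week 4 visit after Day 28, so Days 29-30 arise only from late or unscheduled visits. The 5-D looks back two weeks and the DLQI one week, so a response on those days still mostly describes the treatment period. This stands. The Week 4 half is mainly a matter of disclosure, and no bias has been shown. It does not explain why the Week 8 window became narrower than the protocol's.

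Second, the SAP has no rule that discards a scheduled visit outside its window. A programmer could keep a record labelled Week 8 under that label. This also stands as a possibility, so loss of Day 57-58 data is a literal reading rather than a stated rule. But if the nominal visit label governs, 5.7.1 is not the operative rule and should say so.

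Third, little depends on it: listings keep all data, overall safety summaries include all safety data, and adverse events are analysed to 28 days after the last dose whatever the visit window. That is correct and limits the point to by-visit descriptive and shift tables and the non-NRS by-visit datasets.

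Finally, the conflict between 5.6 and 5.7.1 is a separate defect that would remain with correct windows. Agreed. It may be the more consequential one, since it can change the Week 2 and Week 4 datasets for secondary endpoints.

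**Conclusion.** The concern holds. SAP 5.7.1 takes its windows from a table that contradicts Protocol v3.0 for Week 4 and Week 8, and the difference is undeclared. Two of five permitted follow-up days have no analysis window, and two days beyond the protocol's Week 4 window count as Week 4. Sections 5.6 and 5.7.1 cannot both be followed for unscheduled assessments.

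The day counts follow directly from the two tables. The number of participants is unknown, and the range of 0 to 48 rests entirely on the assumed attendance and timing. The primary analysis and the sample size are untouched. This is a correction that should be made, not one that threatens the trial's main conclusion.

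**What to change.** 1. Reconcile the window row of SAP Table 1 with Protocol v3.0 Table 2, so that every visit day the protocol permits maps to its visit. Windows for Day 1 to Week 3 do not change.
2. If a Week 4 analysis window running past Day 28 is wanted, state it in 5.7.1 and list it, with the reason, in Section 15.
3. State how a scheduled visit outside every window is handled, for example whether it keeps its nominal visit label or is listed only.
4. Choose one rule for unscheduled assessments and write it identically in 5.6 and 5.7.1. One option is to use an unscheduled assessment only when the scheduled one in that window is missing, and to list the rest.

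The cost is a correction to one SAP table and a few sentences, made before unblinding. Trial conduct, data collection and sample size do not change.

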### 5.7.2 Peak Pruritus NRS

The Peak Pruritus NRS is a single self-reported item designed to measure peak pruritus, or ‘worst’ itch, over the previous 24 hours.

On Day 1, pruritus NRS will be assessed at several time points: pre-dose to confirm eligibility and then hourly in the eDiary starting immediately post-dose until bedtime.

Following Day 1, participants will record the peak pruritus NRS daily in the eDiary before the morning investigational product application, and their compliance on the peak pruritus NRS will be followed at each clinic visit. During study visits, the NRS data will be recorded by site staff in the eCRF.

The baseline is Day 1 pre-treatment in-clinic peak pruritus NRS.

Post-treatment daily peak pruritus will be derived as follows:

- The worst hourly pruritus NRS on study day 1.
- First from eDiary data, then diary paper backup, then in-clinic for post study day 1. If there are multiple worst ones, the first one is flagged for analysis. Missing values will not be imputed.

The 7-day daily peak pruritus by week will be the average of all non-missing values from

- NRS week 1: study day 1 post-treatment to study day 7.
- NRS week 2: study day 8 to study day 14.
- NRS week 3: study day 15 to study day 21.
- NRS week 4: study day 22 up to study day 28.

The 7-day average of the Peak Pruritus NRS which is used for primary analysis will be calculated as the average of non-missing values of the daily NRS if there are 50% or more days with non-missing values within each visit window, otherwise it will be set to missing. In addition, any data after the on-study initiation of the prohibited medication will be set to missing values.

The all available 7-day average of the Peak Pruritus NRS which is used for sensitivity analysis will be calculated as the average of all non-missing values of the daily NRS within each visit window. The NRS will be set to missing after the on-study initiation of prohibited medication. If multiple records appear in one source, only the first one will be used for analysis.

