1.1. Study Rationale and Dose Justification

The nonclinical pharmacology data obtained for ASN008 topical gel provide a strong rationale for continued development as a treatment for itch associated with several pathological conditions, such as atopic dermatitis (AD). The data from nonclinical studies with ASN008 topical gel suggested that it was safe and well-tolerated at the doses selected in this trial. Several nonclinical safety pharmacology and toxicology studies via systemic and dermal routes were conducted to support the Phase 1 clinical trial of ASN008 via topical dermal route.

A Phase 1, multicenter, double-blind, randomized, single and multiple ascending doses, vehicle-controlled trial of ASN008 topical gel in healthy volunteers (Part A) and participants with AD (Part B) has been completed (ASN008-101). A total of 32 healthy volunteers were randomized into 4 cohorts in Part A and 25 AD participants were randomized into Part B (10 participants to ASN008 2.46% 2 mg/cm² once daily (QD), 9 participants ASN008 2.46% 2 mg/cm² BID, and 6 participants to placebo).

ASN008 topical gel was well tolerated at all doses following single application on healthy skin (Part A) and multiple applications (QD or BID) on AD lesions (Part B). All treatment-emergent adverse events (TEAEs) reported were of mild severity. No TEAEs at the application area were reported in Part A and only 2 participants (ASN008 BID group) experienced mild TEAEs at the application area in Part B. Both events resolved by the time of trial completion and were considered treatment related. All systemic TEAEs reported were considered not related to the trial product.

Trial results suggest minimal systemic exposure following a single topical application of ASN008 in healthy volunteers, or after repeated (QD or BID topical application of active ASN008 [corresponding to a dose of active moiety of ~49.2 μ g/cm²]) in participants with AD. Preliminary efficacy results showed ASN008 was able to reduce pruritus in AD in participants with a body surface area (BSA) of 1-10%. Participants had a rapid reduction in pruritus following a single application on Day 1, which was sustained up to 8 hours post-dose in QD

participants, and up to 12 hours post-dose in the BID group. The difference between ASN008 QD and vehicle in pruritus was statistically significant on Day 1, at the 4-, 6-, and 8-hour timepoints ($p < 0.05$).

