7.1. Peak Pruritus Numerical Rating Scale

The Peak Pruritus NRS is a single self-reported item designed to measure peak pruritus, or ‘worst’ itch, over the previous 24 h based on the following question: ‘On a scale of 0 to 10, with 0 being “no itch” and 10 being “worst itch imaginable”, how would you rate your itch at the worst moment during the previous 24 hours?’

Participants will be trained on completion of the Peak Pruritus NRS scale at the first Screening Visit before the Peak Pruritus NRS measurements for eligibility are collected.

To be eligible for this study, participants must have a pruritus NRS score of ≥ 7 at screening and Day 1.

On Day 1, pruritus NRS will be assessed at several time points: pre-dose to confirm eligibility and then hourly in the eDiary starting immediately post-dose until bedtime. Following Day 1, participants will record the peak pruritus NRS daily in the eDiary before the morning investigational product application, and their compliance on the peak pruritus NRS will be followed at each clinic visit.

During study visits, the NRS data will be recorded by site staff in the eCRF.

7.2. 5-D Pruritus Scale

The 5-D Pruritus Scale is a 1-page, 5-question, validated questionnaire used in clinical trials to assess 5 dimensions of background itch: degree, duration, direction, disability, and distribution. Each question corresponds to 1 of the 5 dimensions of itch; participants will rate their symptoms over the preceding 2-week period as “present” or on a 1 to 5 scale, with 5 being the most affected. The 5-D Pruritus Scale will be recorded at the visits specified in [Table 2](#).

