## 5 GENERAL CONSIDERATIONS

### 5.1 Sample Size

For the primary endpoint analysis of the percent change of 7-day average daily peak pruritus NRS from Baseline to Week 4, N = 24 / group will give us 80% power to detect a standardized effect of 0.72 with 2-sided significance level of 0.1 (28.8% improvement over placebo in % change from baseline in pruritus, assuming standard deviation [SD] = 40%).

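### The Day 1 daily peak is a maximum that includes the score taken immediately after dosing, which shrinks the Day 1 drug-vehicle difference and, modestly, the Week 1 difference

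*SAP*

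**What the plan says.** SAP 5.7.2 has the NRS assessed before the dose on Day 1 and "then hourly in the eDiary starting immediately post-dose until bedtime". The Day 1 daily value is "The worst hourly pruritus NRS on study day 1"; no hourly score is excluded. From Day 2 the daily value is one morning diary entry, made before application. Protocol 7.1 words the peak item as "how would you rate your itch at the worst moment during the previous 24 hours". Baseline is the in-clinic peak score before the first dose.

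The Day 1 value feeds the weekly average: "NRS week 1: study day 1 post-treatment to study day 7". Week 4 runs from Day 22 to Day 28.

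Change and percent change at Days 1 to 7, and change, percent change and response at Week 1, are secondary endpoints (SAP Table 1, Objectives and Endpoints). SAP 13.2 gives them model-based or exact tests. The protocol also has an exploratory hourly endpoint that starts at Hour 1; SAP 13.3 only summarises and lists hourly scores for Day 1.

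**The concern.** A score given at the moment of application has the same expected distribution in every arm. Inside a mean it would be diluted by the later scores. Inside a maximum it acts as a floor: however far itch falls later in the day, the Day 1 value cannot go below it.

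This affects the evidence on early effect. Protocol 1.1 reports of Phase 1 that "Participants had a rapid reduction in pruritus following a single application on Day 1", so speed of onset is a property this trial would want to show. The Day 1 value is one of the seven daily results in the onset endpoint and one seventh of the Week 1 average.

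A second question is whether the Day 2 entry, which looks back 24 hours, brings early Day 1 itch in again.

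**Working it through.** **The plan's own figure.** SAP 5.1 states that "N = 24 / group will give us 80% power to detect a standardized effect of 0.72 with 2-sided significance level of 0.1", from "28.8% improvement over placebo in % change from baseline in pruritus" and "assuming standard deviation [SD] = 40"%. Using n = 2(z₀.₉₅ + z₀.₈₀)² / d²: 2 × (1.645 + 0.842)² / 0.72² = 23.9, so 24 per group. This reproduces. It concerns Week 4 and is not in dispute.

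**Direction on Day 1.** Let S₀ be the immediate score and M the maximum of the later scores. The Day 1 value is max(S₀, M). For any fixed S₀, raising M by some amount raises max(S₀, M) by that amount or less. If the drug lowers M relative to vehicle, the difference in max(S₀, M) therefore cannot exceed the difference in M. This fails only if treatment worsens itch.

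**Size on Day 1.** The documents give no hourly means or variances, so these inputs are assumptions: 12 hourly scores including Hour 0, mean 6.5, between-person SD 1, independent hourly SD 1.2, scale 0 to 10. Rounding to whole numbers makes no material difference.

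| Onset | True drop | Seen with Hour 0 | Seen without Hour 0 |
|---|---|---|---|
| Complete by Hour 1 | 2 | 1.4 | 1.9 |
| Complete by Hour 1 | 3 | 1.7 | 2.9 |
| Linear over 4 hours | 2 | 1.1 | 1.5 |
| Linear over 4 hours | 3 | 1.4 | 2.0 |

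A second set of assumptions used a 28.8% reduction, linear onset over 1 to 4 hours, 10 or 14 scores and hourly autocorrelation of 0.3 to 0.8. Day 1 keeps 51% to 77% of the full effect as written, and 68% to about 100% without Hour 0.

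**Size in Week 1 from Day 1 alone.** If Day 1 shows a share r of the effect and the other six days show all of it, Week 1 keeps (r + 6)/7.
- 2-point drop, complete by Hour 1: r = 1.4/2 = 0.70, giving 6.70/7 = 0.96.
- 3-point drop, complete by Hour 1: r = 1.7/3 = 0.57, giving 6.57/7 = 0.94.
- Limit at r = 0: 6/7 = 0.86, a loss of 1/7.

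**What that means for power.** Take 28.8 points as the full daily effect and SD 40 at Week 1 (both borrowed from the Week 4 rationale), with 30 per arm and two-sided 0.05. Power is Φ(Δ / (40√(2/30)) − 1.96).
- No loss: Δ = 28.8, power 0.80.
- Retention of 0.94 to 0.96: Δ = 27.1 to 27.6, power about 0.75 to 0.76.
- Limit at 6/7: Δ = 24.7, power 0.67.

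**The Day 2 entry.** Let the Day 1 dose be at clock time a and the Day 2 entry at clock time b. The recall starts at time b on Day 1. If b is earlier than a, it reaches itch before the first dose. If b is well after a, it misses the early hours. Neither document gives a or b. In the second set of assumptions:
- With instantaneous onset and no reach before the dose, Week 1 keeps 1.00. Covering Day 1 twice is then only a weighting.
- With onset over 1 to 4 hours and a recall reaching 0 or 2 hours before the dose, Day 2 keeps 43% to 83% and Week 1 keeps 85% to 94%.

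**Within-arm change.** Baseline is a 24-hour peak, while the Day 1 value covers waking hours after the dose. In the simulated vehicle arm the Day 1 maximum lies 0.3 to 0.6 points below a 24-hour peak with no drug effect at all. This pushes change from baseline away from zero, against the pull of the immediate score.

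**The case against.** The strongest case against acting is that the outcomes are secondary in a Phase 2 trial, the between-arm error is conservative, and the Week 1 loss is a few percent. All of that stands, and it is why the point is minor. It is also fair that removing Hour 0 does not cure a gradual onset: Protocol 1.1 names significant differences at 4, 6 and 8 hours and no earlier time, and the four-hour rows above show much of the loss remaining.

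A reader might infer more than the documents support:
- **That covering Day 1 twice is itself a bias towards zero.** It is a weighting. It attenuates only if the Day 1 effect is smaller than later effects or the Day 2 recall reaches hours before the drug acts. Protocol 6.1 asks for applications at about the same times each day, so a large overlap cannot be assumed.
- **That Week 1 loses a tenth or more.** That needs a substantial Day 2 loss, which rests on unknown clock times.
- **That the rule distorts the active arms and spares vehicle.** Protocol 9.3.1 assumes a 10% vehicle effect, and the immediate score hides part of that too. What shrinks is the difference between arms.
- **That no other onset measure exists.** Hourly NRS avoids the maximum. The SAP gives it no test, although Protocol 9.3.1 would analyse other continuous variables like the pruritus score.
- **That Week 1 should be rebuilt without Day 1.** Both documents define a 7-day average, and dropping one day outright is debatable. It fits better as a sensitivity analysis.

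**Conclusion.** The point holds in a limited form. As written, the Day 1 peak includes a score the drug cannot have affected, and this attenuates the active-minus-vehicle difference on Day 1. The direction needs only that treatment does not worsen itch. The size depends on assumed hourly variability and onset: in the first simulation, 2- and 3-point drops complete by Hour 1 show as 1.4 and 1.7.

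The Week 1 loss from Day 1 alone is about 4% to 6% under those inputs and cannot exceed 1/7 if the effect is equal on the other six days. Any further loss through Day 2 is possible but unsettled. The sign of within-arm change from baseline is uncertain. The Week 4 outcome uses no post-dose value from Days 1 or 2, and the sample size stands.

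One gap could change the size. The recall wording of the hourly item is not stated. If it uses the 24-hour wording, every Day 1 score carries pre-dose itch, and Day 1 could lose nearly all of its effect.

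**What to change.** In SAP 5.7.2:
1. Derive the Day 1 daily peak from scores at Hour 1 and later, in line with the protocol's hourly endpoint.
2. State the recall wording of the hourly item.
3. Keep the 7-day Week 1 average, and add a prespecified Week 1 sensitivity analysis that omits Day 1 and any Day 2 entry whose 24-hour recall reaches before the first dose. State how the 50% completeness rule applies to the remaining five or six days.

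Under the second set of assumptions with onset over 1 to 4 hours, averaging the Day 2 to 7 entries keeps about 90% to 97% of the effect: (0.43 + 5)/6 to (0.83 + 5)/6. Where the recall does not reach before the dose, Day 2 keeps 70% to 83%, and the average keeps 95% to 97%.

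The cost is derivation text, one fewer hourly score on Day 1 and one extra table; no new data are needed. With gradual onset some attenuation remains, and the report should say so. This is a cheap improvement of minor severity.
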